6.1 Name and description of intervention yoghurts

The active intervention product will be a low-fat yoghurt (120 g, Campina, Magere yoghurt, 0% fat) mixed with 60 gram 'encapsulates' (gel particles that encapsulate safflower oil in such a way to deliver into the ileum). These encapsulates compose for 88 wt% of water (52.9 g per 60 g gel particles), and contain 2 wt% alginate (1.08 g per 60 g gel particles) and 10 wt% safflower oil (6 g per 60 g gel particles, present as droplets with average size of 25 μm). The active intervention yoghurts contain 105 kcal; of which 51 kcal% comes from the lipid (see Table 2).

Control product will be the same low-fat yoghurt as the active product, containing the same components as the 60 gram encapsulates, only with different physical structure: 54 gram empty gel particles (1.08 g alginate) present separately from 6 g safflower oil (same droplet size as in encapsulate). The control yoghurts also contain 105 kcal; of which 51 kcal% comes from the lipid (see Table 2).

Table 2. Overview of the nutrient composition of the studied formulations, and caloric content.

Name	Yoghurt A	Yoghurt B
	Active	Control

Safflower oil (g)	6.0	6.0
Whey protein (g)	0.24	0.24
Alginate (g)	1.08	1.08
Water inter-/intra-gel (g)	76.9	76.9
Yoghurt (g)	120	120
Total (g)	204	204
Total (kcal)	105	105
Lipid contribution (kcal%)	51%	51%

6.2 Summary of findings from non-clinical studies

Lipolysis has been controlled *in vitro* by lipid encapsulation in both digestible protein gels [22], [23] and indigestible alginate gels [24], [25]. The latter is the approach taken in the current study given the resistance of alginate matrix against gastric proteases [23], so ensures maintenance of the encapsulate structure in the stomach. In addition, the pH-dependency of volume and porosity of alginate gel particles makes them very suitable for ileal delivery [24], [26]–[28].

We designed encapsulates of safflower oil droplets (S) ($d_{32} \sim 25 \mu\text{m}$) in Ca-alginate (CA) hydrogel particles (0.5-1.2 mm) with different pore size of the hydrogel (5-10 nm). Lipolysis was controlled simply by gel particle size, and pore size at neutral pH, as shown for studied in a simple static *in vitro* digestion model. As preparation for the current human trial, we added these S-CA particles to yoghurt-meals and studied lipolysis during dynamic *in vitro* digestion in a three-compartment model of the upper GI tract (DIDGI, [36], [37]). Digestive media was sampled and analysed both for total extent of lipolysis and for the fraction solubilised in mixed bile micelles. To distinguish between i) direct inhibition of lipase by alginate [38] and ii) physical barrier to encapsulated oil [24], meals containing S-CA particles were compared to control meals with non-encapsulated lipid droplets, both in the presence and absence of empty CA particles. Lipolysis of non-encapsulated lipid was fast and would correspond to time scales relevant for duodenal delivery, whereas encapsulated lipid in CA particles showed delayed lipolysis up to four hours after ingestion, corresponding to ileal delivery.

6.3 Summary of findings from clinical studies

Ileal brake activation has been proven to be effective with direct intubation of all three macronutrients *via* a naso-ileal catheter (overview of literature in [3]). About 30 years ago, ileal lipid infusion was already shown to reduce food intake [4], [5]. Moreover, ileal lipid infusion increased perception of satiety/fullness or decreased hunger in most studies [1], [2], [4]–[7].

Regarding the current product, all ingredients (whey proteins, alginate, calcium, safflower oil) are commercially available food products with bio-base (so no synthetic additives), and have been repeatedly used in previous human trials (just some examples: alginate [29]–[33], calcium [29], [35], whey proteins even in infants [39], safflower oil [1], [6], [40]). Alginate as such has been used in clinical trials in multiple formulation forms, and it might reduce feelings of hunger (especially when present in solution) or have no effect [29]–[33].

Relatively large Ca-alginate gel particles (3.9-4.4 mm) have been tracked using MRI scanning in the human GI system (n=10) and were more visible in the ileum compared to the jejunum and duodenum [29]. This suggest an extended residence time in the ileum, and therefore favours ileal brake activation.

One human trial has been performed on an encapsulation system containing similar components: oil-core calcium-alginate-shell capsules (0.5 cm), which resulted in faster gastric emptying, and delayed lipolysis and absorption as measured with ¹³C-labelled octanoic acid detected in a breath test [35], though these capsules would be quite large to use as a food additive.

6.4 Summary of known and potential risks and benefits

In our previous experiments with ileal brake activation *via* nutrient delivery through an ileal catheter, high distal ileal nutrient concentrations have been reached. However, none of the subjects experienced any discomfort during or after direct infusion into the ileum. We do not anticipate on major complaints or side effects for the current study with oral application route and therefore less pronounced ileal nutrient concentrations.

Besides, potential risks are expected to be minimal: First, a commercially available low-fat yoghurt (Campina, Magere yoghurt, 0% fat) will be used. Second, all of the added components are commercially available food ingredients with bio-base (so no synthetic additives) that have been repeatedly used in previous human trials. These include: alginate[29]–[33], calcium [29], [35], whey proteins [39], safflower oil [1], [6], [40]). Thus, all ingredients have a documented history of safe use. As mentioned previously, only for alginate we foresee a possibility for GI symptoms, for example abdominal bloating (3 out of 48 participants); but no significant difference (in nausea, fullness, bloating and pain scores) were detected compared to placebo [33]. Although alginate is used for multiple human applications (*e.g.*, acid burn), it may cause discomfort and/or GI symptoms due to viscosity-induced delay of the GI transit. To minimize possible discomfort and GI symptoms, the study will be halted when pain (as burning/cramp/colic) is measured to be extremely unpleasant (VAS scores > 95 out of 100) in three or more subjects.

6.5 Description and justification of route of administration

The lipids will not be administered *via* an ileal catheter, as the effectiveness of this administration route has been proven already in previous studies (for an overview of studies, we refer to the review [3]). For an effective weight management strategy, administration should be performed *via* the normal route of food intake: oral administration. The current study will focus on the ability of lipid to induce the ileal brake when given orally. The lipids will be mixed with yoghurt, not only to allow easy consumption for the participants, but also to ensure no difference in appearance between control and active formulation. The lipids from the active intervention yoghurt will be delivered into the more distal small intestine within the two hours between ingestion and meal intake, and might consequently activate the ileal brake, whereas the control intervention yoghurt will deliver nutrients more proximally (to the stomach and duodenum). This allows investigating the effects of distal small intestinal delivery of undigested nutrients on food intake.

6.6 Dosages, dosage modifications and method of administration

To determine the dosage, we combined knowledge on effective dosage upon direct ileal fat perfusion with knowledge on the release profile of the current encapsulation system. Previous ileal brake studies have shown no dose dependency of satiety between 3 g and 9 g [6]. The current encapsulation system is expected to deliver at least 50% of the encapsulated lipid into the ileum, based on *in vitro* release data from static and dynamic digestion models (as summarized in section 1 and 6.2). We chose the investigational products to contain as little lipid as possible to still be effective, because lipid is a highly caloric nutrient and difficult to be compensated in the subsequent lunch. Therefore, the intervention yoghurts contain 6 grams of encapsulated safflower oil to release ≥ 3 g into the ileum ($\geq 50\%$).

The method of administration of the active is based on an encapsulation method, using a matrix of alginate that is gelled by calcium divalent ions. The release of encapsulated lipid from these gel particles is based on pH-induced swelling at neutral pH as in the small intestine. This swelling increases the porosity of the gel matrix, which favours diffusion *via* increasing its coefficient. We found this diffusion coefficient under *in vitro* intestinal conditions to determine the release rate. By reverse engineering, we designed encapsulation systems that encapsulate safflower oil, and tuned the release profile based on gel matrix.

6.7 Preparation and labelling of Investigational Product

Handling and labelling will be done in the food facility of the Metabolic Research Unit Maastricht (MRUM, Maastricht University), following relevant HACCP guidelines. All ingredients (whey proteins, alginate, calcium, safflower oil) are commercial available food products, so no special precautions have to be taken in handling of the substances (see section 12 for a structured risk analysis). The alginate gel particles, both empty and filled with lipid, will be produced in accordance with safety and quality regulations of the commercial manufacturer. After preparation of these particles, they will be stored not longer than four days (96 hours) in 0.5 M CaCl₂ solution under refrigerated conditions (temperature of 4 °C) to ensure microbial safety. The ingredients (*i.e.*, yoghurt, oil-gel particles, or gel particles and emulsion) will be mixed freshly (1 to 20 hours before consumption) and stored under refrigerated conditions as suggested by the yoghurt supplier (Campina, Magere yoghurt, 0% fat). A detailed description of the procedures can be found in a separate standard operating procedure for the active and control yoghurt.

Labelling of the products will be according to the following code: study title (Lipid encapsulates, LE), subject number (01-35), yoghurt (A, B), and date. For example: LE07/A 13-02-17 means subject 7 of lipid encapsulates study-yoghurt A (active) produced on February 13th 2017.

6.8 Drug accountability

Not applicable as all used substances are food grade.

7. METHODS

7.1 Study parameters/endpoints

7.1.1 Main study parameter/endpoint

The main study parameter is the intake of *ad libitum* meal (kcal), as measured during pasta lunch (based on weight reduction of the plate assuming a homogenous meal). The reduction in amount of intake is supposed to reflect the activation of the ileal brake. The food intake will be compared between encapsulated lipids (active, yoghurt A) and non-encapsulated lipids in a formulation with equal nutrients (control, yoghurt B) within a subject.

7.1.2 Secondary study parameters/endpoints

Feelings of satiety (VAS scores)

The secondary study parameter is the effectivity to activate the ileal brake and, hence, induce feelings of satiety and reduce feelings of hunger, as measured on VAS scores (satiety, fullness, hunger, desire to eat, desire to snack). The VAS scores will be compared in time between intervention and control within a subject.

GI symptoms (VAS scores)

Another secondary study parameter is the occurrence and severity of gastrointestinal (GI) symptoms that orally ingested lipid encapsulates might give, as measured on VAS scores of GI symptoms (bloating, discomfort, pain, nausea). The VAS scores will be compared in time between intervention and control within a subject. Besides, the number of AEs and SAEs will be recorded. Moreover, we will assess whether differences in GI symptoms relate to encapsulate type.

7.2 Randomisation, blinding and treatment allocation

All 35 participants receive two treatments of one day each, following a cross-over design. The order in which they receive the treatments will be determined through randomisation. Randomisation will minimize the risk of bias and enhance the validity of statistical comparisons. As subjects qualify for the study, they will be assigned a subject number (01 - 35, *via* lottery) that corresponds with a predefined randomization schedule.

Blinding of packing and treatment will be assured for subjects. We will check at the end of the last test day whether the subjects were expecting to consume a control on one or more of the test days, and in case yes, on which day(s) they received it. Besides, on this day we will ask how they liked the yoghurts.

The VAS questionnaires will be labelled by the researcher with study title (Lipid encapsulates, LE), subject number (01-35), yoghurt (A, B) and time point (t= 0, 30, 60, 90, 105, 120, 135, 150, 165, 180, 195, 210 min). For example: LE07/ A / 120 - Subject 07, active yoghurt, VAS scores at 120 minutes.

Besides, labelling of the products will be according to the following code: study title (Lipid encapsulates, LE), subject number (01-35), yoghurt (A, B), and date. For example: LE07/A 13-02-17 means subject 7 of lipid encapsulates study-yoghurt A (active) produced on February 13th 2017.

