Upon arrival at Maastricht University (8:50 am), compliance to the previously mentioned rules will be checked and baseline measurements will be done ("t=0" min), including nine VAS scores for satiety and GI symptoms. Then, the experiment starts with the ingestion of a standardized breakfast (9:00 am, t=0 min). During all study days, this breakfast will be relatively light (± 120 kcal) and low in fat (≤ 0.5 g total lipid): 1 sandwich (tijgerbrood tarwe 1 g lipid/100g, 1 boterham: 35g (± 84 kcal)) with marmalade (0 g lipid/100g, 1 portion: 15g (± 36 kcal)) and one glass of water or tea (150 mL).

Ninety minutes after breakfast (10:30 am, t=90 min), once major part of the breakfast has been emptied from the stomach, subjects receive a low-fat yoghurt-like product of 0.20 L that contains one of the two formulations of emulsified safflower oil (6 g lipid as active or control formulation, for product details see section 5), following a randomized cross-over design. Each 30 minutes before the intervention and each 15 minutes after the intervention, the nine VAS scores for satiety and GI symptoms will be measured. Two hours after the intervention yoghurt (12:30, t=210 min), *ad libitum* meal intake will be measured as amount eaten from a large pasta meal (>1 kg, obtained from a local supermarket). After collection of these results, the test day is finished and the subject returns home (around 13:00 am). For an overview of the complete study design, see Figure 1.

VAS scores for satiety and GI symptoms- During a test day, satiety and GI symptoms will be measured at 12 time points (t= 0, 30, 60, 90, 105, 120, 135, 150, 165, 180, 195, 210 min). Questionnaires will be used to measure satiety feelings (satiety, fullness, hunger, desire to eat, desire to snack) and GI symptoms (bloating, discomfort, pain, nausea). These nine attributes will be measured using Visual Analogue Scales (VAS, 0 to 100 mm) scores, with the most negative or lowest intensity feelings at the low end and the opposing terms at the high end. The subject will be asked to indicate his feeling at that moment. The investigator can easily quantify the rating as shown in previous studies (for example: METC 13-2-025; 11-3-034; 14-3-062). The scoring forms will be collected immediately so that they cannot be used as a reference for later scorings.

Table 3. Schedule of the participant prior and during the test days.

When?	Action/Intervention	Measurement

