9. STATISTICAL ANALYSIS

The SPSS statistical software package Version 23.0.0.2 (IBM[®] SPSS Statistics, Chicago, IL, USA) will be used for statistical analysis. The data will be organized in this software, containing descriptive independent variables (ID, age, gender, BMI), fixed variables (test day (1, 2), treatment (A, B), time) and dependent variables (food intake and VAS scores). A descriptive analysis of the study population will be performed first, about the independent variables age, gender and BMI, including mean \pm S.D. The dependent variables will be checked to meet the requirements of the statistical models described, including and normality, and homogeneity of variance. Continuous data will be reported as mean \pm S.D and/or S.E.M. and statistical significance will be set at $p < 0.05$, two sided.

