11. ADMINISTRATIVE ASPECTS, MONITORING AND PUBLICATION

11.1 Handling and storage of data and documents

Data are handled confidentially and anonymously in accordance to WBP (in Dutch: Wet Bescherming Persoonsgevens; Personal Data Protection Act). To guarantee the privacy of the participants, subject numbers will be used in such a way that no personal information about the participants will be available (allocated *via* lottery). All questionnaires and data will be coded (using study title (Lipid encapsulates, LE), and subject number (01-35), yoghurt (A, B) and time point (t= 0, 30, 60, 90, 105, 120, 135, 150, 165, 180, 195, 210 min). For example: LE07/ A / 120- Subject 07, active yoghurt, VAS scores at 120 minutes. The researcher keeps the key of the code in a locked cabinet. Next to the research team, the data is assessable for the METC, IGZ and monitors. No human material will be taken during this study. All primary documents and data shall be kept for 15 years after the end of the experimental phase of the study for possible inspection. All future studies will always be sent to the METC for approval.

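### VAS forms and VAS data codes carry a fixed arm letter (A = active for all 35 subjects) that they do not need; labelling by test day is a cheap improvement, not the repair of a broken blind

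*Combined protocol and SAP*

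**What the plan says.** All references are to the combined protocol and SAP.

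- **Form label.** Section 7.2: "The VAS questionnaires will be labelled by the researcher with study title (Lipid encapsulates, LE), subject number (01-35), yoghurt (A, B) and time point". Its worked example is decoded as "Subject 07, active yoghurt, VAS scores at 120 minutes".
- **Data code.** Section 11.1: "All questionnaires and data will be coded (using study title (Lipid encapsulates, LE), and subject number (01-35), yoghurt (A, B) and time point".
- **Meaning of the letter.** Table 1 and Sections 6.7 and 7.1.1 define A as active and B as control for the whole study. There is no subject-specific code.
- **Scope of the blind.** Section 3 declares the trial single-blind, and Section 7.2 says "Blinding of packing and treatment will be assured for subjects". No blinding of the person who reads the forms, enters the data or analyses them is promised.
- **Handling of the forms.** Section 7.3 says "The investigator can easily quantify the rating as shown in previous studies" and, as a safeguard, "The scoring forms will be collected immediately so that they cannot be used as a reference for later scorings".
- **Other identifiers already planned.** Section 9 lists "fixed variables (test day (1, 2), treatment (A, B), time" among the data-file variables. Section 7.2 gives each subject a number "that corresponds with a predefined randomization schedule".
- **Check on the subject blind.** At the end of the last test day, subjects are asked whether they expected a control and, if so, on which day (Section 7.2).

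**The concern.** The secondary outcomes are self-reports. Satiety rests on the VAS forms alone, and GI symptoms rest on the forms plus recorded adverse events (Section 7.1.2). Section 12.1(i) confirms that no biomarkers are used. If knowledge of the arm affected how marks were made or read, no objective secondary measure would reveal it.

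The plan already treats these forms as open to bias, since Section 7.3 removes each one at once so that it cannot anchor the next rating. The arm letter nevertheless stays on the same sheet. Because it means the same for everyone, it is also fragile: if its meaning became known, it would decode the forms of all 35 subjects.

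The letter might reach two people. The investigator who quantifies the mark sees it in every case. The subject sees it only if the label is applied before the form is completed, and the document does not give that order.

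**Working it through.** The plan states no figure on this point, so there is none to reproduce. The check has three parts.

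**1. How many forms carry the letter.** Inputs: 35 subjects and 2 treatment days (Section 7.2), 12 time points per day (Section 7.3), and 9 ratings per form, of which 5 concern satiety and 4 GI symptoms (Section 7.3). Table 3 notes that the t = 90 form is completed just before the yoghurt.

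- All forms: 35 x 2 x 12 = 840.
- Before the yoghurt (t = 0, 30, 60, 90): 35 x 2 x 4 = 280.
- After the yoghurt (the other 8 time points): 35 x 2 x 8 = 560.
- Ratings after the yoghurt: 560 x 9 = 5,040 (560 x 5 = 2,800 satiety and 560 x 4 = 2,240 GI).

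These are planned maxima, reached only if all 35 subjects complete. With the 31 completers that Section 4.4 requires, and counting completers only, there would be 31 x 2 x 12 = 744 forms. The counts measure exposure to the label and say nothing about bias.

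**2. Whether the forms can be told apart without the letter.**

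- Subject x letter x time point: 35 x 2 x 12 = 840 distinct codes.
- Subject x test day x time point: 35 x 2 x 12 = 840 distinct codes.

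Each subject is scheduled to receive each yoghurt once. For any randomisation schedule, subject plus test day therefore leads to exactly one scheduled yoghurt, and the two codes map one to one.

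**3. Whether the two codes carry the same information.** They do not quite. The mapping in step 2 assumes that the yoghurt served was the one scheduled. The letter is meant to tie the form to a yoghurt. The test-day number gives only the schedule, so after a serving mix-up it would return the wrong arm. This matters here because the two products are made to look alike (Section 5.1) and drug accountability is set aside as not applicable (Section 6.8). A test-day label therefore needs a separate record of what was served: at most 35 x 2 = 70 entries.

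**The case against.** The strongest case on the other side runs as follows.

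- **The design permits it.** Single-blind here means blinded subjects, so staff may know the arm. This stands. A reader might infer that the labels break the blind, but the document does not support that. Nothing in it says that subjects are told what A and B mean, and a bare letter does not tell them.
- **The subject blind is protected and checked.** The yoghurts are matched in appearance and mouth feel (Sections 5.1 and 5.2), and the end-of-study question would partly detect a leak. This stands for subjects. The question does not cover the person reading the forms.
- **Little judgement is left to the reader.** The subject makes the mark and the investigator measures it on a 0 to 100 mm line. This largely stands, and it keeps the likely gain small.
- **The change may mask little.** No section separates the reader from the staff who prepare or serve the yoghurt. This also stands: for a reader who knows the day's yoghurt, a neutral label hides little.
- **Something is lost.** A reader might infer from 840 codes against 840 that the swap costs no information. Step 3 of the working shows otherwise, and the served-yoghurt record is the price.

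These objections limit the weight of the point. They give no reason to keep the letter on the form, where an identifier already in the plan can replace it.

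**Conclusion.** The point holds as a small, inexpensive improvement to the labelling of the VAS forms and VAS data codes. The letter is not needed there. It shows the arm to the person quantifying self-reported ratings, and it gives one common key for all 35 subjects. It affects up to 840 forms, of which up to 560 are completed after the yoghurt.

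The size of any bias cannot be estimated from the document, and nothing shows that bias would occur. Exposure of subjects depends on when the forms are labelled, which is not stated. The benefit for reading depends on the reader not otherwise knowing the arm.

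A reader might extend the point to the primary outcome. The document does not support that: intake is taken from the weight lost from the plate (Section 7.1.1), and no argument here concerns the handling of intake data. Nor does any section link withdrawal decisions to form labels. Sample size, alpha and power are unaffected.

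**What to change.** 1. In Sections 7.2 and 11.1, label VAS forms and VAS data codes with subject number, test day (1 or 2) and time point, for example LE07/day 1/120. State whether forms are labelled before or after completion.
2. Quantify the forms under that code and add treatment afterwards.
3. Keep the A/B letter on the yoghurt packs, but state that subjects do not see it.
4. Record for each subject and test day which yoghurt was actually served, and take treatment from that record, checked against the randomisation schedule.
5. Do not claim blinded reading in the report if the reader also served the yoghurt or held the schedule.

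**Cost.** The change needs new label text, a record of at most 70 entries and one merge step, with no extra visit, measurement or product. The separate product procedure mentioned in Section 6.7 was not available to check and may already contain such a record. The pain-based halt in Section 6.4 counts subjects without reference to arm, so the neutral code does not hinder it.
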